#### 10.1.3 Procedure for handling missing data

Safety: The safety assessment will include in the analysis all subjects (both eyes) who have been exposed at least once to any of the interventions. Subjects enrolled in the efficacy phase will be included in the safety analysis for this phase, regardless of the visit at which they were eliminated from the study (ITT; intention-to-treat population).

Efficacy: Subjects who meet a minimum adherence of 70% will be included in the statistical analysis to meet the study objective, based on the weight of the PI. In cases where the container is not returned or has not been physically intact, adherence will be measured using the subject's diary.

#### 10.1.4 Deviations from the statistical analysis plan

According to the sample size calculation to meet the efficacy objective, 102 evaluable subjects (51 subjects per arm) are required. If this number is not met due to a loss of subjects exceeding the 20% threshold established in this protocol (loss to follow-up or withdrawal from ICF), as mentioned in section 5.3.1, in order to balance the treatment groups, the sponsor may substitute these subjects.

The results obtained from the replaced subjects will continue to be used for safety analysis and will be part of the ITT.

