## 1.1 Synopsis

Title of the study: Phase I-II clinical study to compare the safety and efficacy of Nanodrop® versus Systane® Balance in the treatment of patients with dry eye	
Study number: SOPH176-1218/I-II	Creation date: December 11, 2018
Protocol version: 1.0	Version date: 11-dic.-18
Therapeutic indication: Lubricante ocular	Use: Ojo seco
Estimated duration of the study (from the first visit of the first patient to the preparation of the final report) : 11 meses	Development phase: I-II
Goals: Security: To evaluate the safety of ophthalmic application of Nanodrop® by quantifying the incidence of unexpected Adverse Events (AEs) related to the investigational product (IP).	
Effectiveness: To demonstrate the non-inferiority of Nanodrop® compared to Systane® Balance in the treatment efficacy of patients with dry eye, using the OSDI (Ocular Surface Disease Index) test score.	
Hypothesis: Security: $H_0$ = Nanodrop® is safe in its ophthalmic application, presenting an incidence of unexpected AEs, related to the PI less than 20% of the population of the Nanodrop® safety group $H_1$ = Nanodrop® is not safe for ophthalmic application, as it presents an incidence of unexpected AEs related to the PI greater than 20% of the population in the Nanodrop® safety group. Effectiveness: $H_0$ = Nanodrop® is inferior to Systane® Balance by more than 5 points on the OSDI test score $H_0: \mu_A - \mu_B > \delta$ $H_1$ = Nanodrop® is inferior to Systane® Balance by 5 points or less on the OSDI test score $H_1: \mu_A - \mu_B \leq \delta$	
Study design: Phase I-II, comparative, non-inferiority, active-controlled, parallel-group, double-blind, randomized clinical trial. Safety analysis is performed upon completion of the first 12 subjects in the Nanodrop® group. If fewer than 20% of unexpected adverse events (AEs) related to the investigational product occur, recruitment continues until the sample size for the efficacy analysis is complete.	
Number of subjects: n= 126 evaluable subjects 63 evaluable subjects per group (both eyes).	Main inclusion criteria: Diagnóstico de ojo seco
Selection criteria :	

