## 10.2 Sample size calculation

### 10.2.1 Number of subjects calculated

n= 126 evaluable subjects (both eyes)

63 subjects per arm.

An estimated 63 subjects (both eyes) are enrolled per treatment arm. During the safety phase, 24 subjects (12 from each group) will be recruited, and 102 will be recruited during the final phase, completing the sample of 126 required for the efficacy analysis.

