The sample size calculation was performed considering a reduction in the OSDI score of 17.6 points for the placebo group at their final visit versus a reduction of 16.5 points for the treated group. Considering a δ of 17.1, a similar reduction in the OSDI score is expected for both treatments, with no statistically significant differences at their final visit.

The calculation was performed using the online tool: <http://powerandsamplesize.com>.

The estimated sample size was 101 subjects (51 subjects per arm), which was increased by 25% to account for potential losses (25 subjects). The estimated number of subjects (both eyes) was 126.

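### The protocol gives both 126 and 102 as the evaluable number for the same objective; 126 is the enrolment figure, and the replacement rule leaves out the adherence exclusions that shrink the efficacy set

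*Protocol*

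**What the plan says.** **Sample size.** The synopsis gives "n= 126 evaluable subjects" and "63 evaluable subjects per group (both eyes)". Protocol 10.2.1 repeats 126 as evaluable. It then says that 63 per arm are enrolled, 24 in the safety phase and 102 in the final phase, "completing the sample of 126 required for the efficacy analysis". Protocol 10.1.4 attributes a different figure to the sample size calculation: "102 evaluable subjects (51 subjects per arm) are required".

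SAP 5.0 shows how the figures are related: "The estimated sample size was 101 subjects (51 subjects per arm), which was increased by 25% to account for potential losses (25 subjects)", giving 126.

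**Replacement.** Protocol 10.1.4 lets the sponsor substitute subjects if the 102 is missed because losses exceed 20%. It counts as losses only "loss to follow-up or withdrawal from ICF". Section 5.3.1 limits replacement to the same two groups.

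**Efficacy set.** Protocol 6.4, 10.1.3 and 10.1.5, and SAP 7.0, restrict the efficacy analysis to subjects with at least 70% adherence. Those below 70% are kept for safety only.

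**The concern.** One label and one objective carry two numbers. The evaluable count is what a reader uses to judge whether the efficacy analysis has the size that was planned. Calling 126 evaluable hides the loss allowance that the SAP built into that figure.

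The safeguard for the target also counts something different from the target. A subject below 70% adherence leaves the efficacy analysis, but is neither counted toward the 20% condition nor replaceable. Subjects eliminated under 5.2.1 for a serious adverse event or intolerance are not named in the condition either. The number analysed can thus fall below the stated requirement with the plan silent on it.

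**Working it through.** **1. Reproduce 126.**
- 101 × 1.25 = 126.25, and 101 / 0.80 = 126.25. Both give 126, so it is an enrolment number derived from 101.
- 51 per arm is 102, one more than the SAP's total of 101. The allowance is therefore 126 − 101 = 25 or 126 − 102 = 24 subjects.
- The 102 recruited in the final phase (10.2.1) is 126 − 24. It is a different quantity that happens to equal the 102 evaluable.

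**2. Test the 20% condition**, assuming that its denominator is the 126 enrolled (10.1.4 does not say).
- 20% of 126 is 25.2, so the condition is exceeded only from 26 losses.
- 25 losses: 25/126 = 19.8%, and 126 − 25 = 101. This is below 102 with the condition not met and before any adherence exclusion.

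**3. Add adherence exclusions.** The documents give no rate, so these are assumptions, applied to the subjects who remain.

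| Counted losses | Assumed non-adherence | Efficacy set | 20% exceeded? |
|---|---|---|---|
| 0% | 20% | 126 × 0.80 = 100.8 | No |
| 5% | 15% | 126 × 0.95 × 0.85 = 101.7 | No |
| 10% | 10% | 126 × 0.90 × 0.90 = 102.1 | No |
| 10% | 15% | 126 × 0.90 × 0.85 = 96.4 | No |
| 15% | 15% | 126 × 0.85 × 0.85 = 91.0 | No |

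**4. Check whether 102 carries the stated power.** Inputs from Protocol 10.2.2 and SAP 5.0: SD 17.1 (the SAP prints the symbol as δ), margin 5 points, α 0.05 with z(1−α), so one-sided, power 80%, and reductions of 17.6 and 16.5, a difference of 1.1. Allocation is 1:1 (SAP 7.0). The documents label those reductions placebo and treated, so all directions are shown.

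The documents' formula with k = 1 is n per arm = 2 × [17.1 × (1.645 + 0.842) / D]², where D is the distance from the assumed difference to the margin.
- Favourable to the test product, D = 6.1: 97.2, so 98 per arm.
- No difference, D = 5: 144.6, so 145 per arm.
- Unfavourable, D = 3.9: 237.7, so 238 per arm.

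None gives 51 per arm. With the difference rounded to 1.0 in the favourable direction (D = 6.0) the result is 101 per arm, which equals the SAP's stated total. A per-arm figure may have been read as a total, but the documents do not show the step.

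Power at 51 per arm: SE = 17.1 × √(2/51) = 3.386, and power = Φ(D/SE − 1.645). The second term of the documents' power formula adds less than 0.3 percentage points.
- D = 6.1: Φ(1.801 − 1.645) = 56%.
- D = 5: Φ(1.477 − 1.645) = 43%.
- D = 3.9: Φ(1.152 − 1.645) = 31%.

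At 63 per arm the same calculation gives 64%, 50% and 36%. If the 95% CI named for non-inferiority is two-sided (one-sided 0.025), power at 51 per arm is 44%, 31% and 21%.

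**The case against.** The other side has a good case on consequences. SAP 5.0 explains the two numbers, and 126 is the recruitment figure wherever it is put to use: the recruitment rate in Protocol 4.3, the six centres at 21 subjects each in 5.5 (6 × 21 = 126), and the enrolment sentence in 10.2.1. The word evaluable is never formally defined, so equating it with the set at 70% adherence or above is an inference. Replacement is at the sponsor's discretion, so nothing happens automatically even for counted losses. The SAP's allowance is for losses in general and could absorb adherence exclusions. Not replacing non-adherent subjects is defensible: adherence arises after randomisation, and bottle weight, the main measure, is known only once the container is returned.

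All of that stands, and it rules out two stronger readings. A reader might infer that a trial with 102 in the efficacy set is 24 subjects short, or that 126 evaluable would require about 158 randomised at 20% loss (126/0.8 = 157.5). Both treat 126 as a true evaluable target, which SAP 5.0 excludes. Recruitment is 126 on either reading.

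The objection does not remove the defect. The synopsis and 10.2.1 still misstate the evaluable number. The inference about evaluable is well supported, because 10.1.4 ties the word to the efficacy objective and 10.1.5 says who is analysed for that objective. Section 5.3.1 gives completing the minimum efficacy population as a purpose of replacement, but does not widen who may be replaced. No passage says that the allowance covers non-adherence.

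**Conclusion.** The point holds as a mislabelled sample size and an incomplete count. The evaluable number implied by the documents' own derivation is 101 to 102, and 126 is enrolment. The efficacy set can fall below 102 without the 20% condition being met: to 101 through counted losses alone, and to about 96 with 10% loss and 15% non-adherence. The second figure rests on an assumed rate; both rest on 126 as the denominator and on evaluable meaning the efficacy set.

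A reader might also infer that settling on 102 secures 80% power. It does not: under the stated inputs power at 51 per arm is about 56% at best, and 126 analysed would reach about 64% at best. The base sample size is a separate and larger matter, and correcting the labels should not be taken as endorsing 102.

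**What to change.** - **Synopsis and Protocol 10.2.1:** call 126 (63 per arm) the number randomised. Remove the word evaluable and the statement that 126 is needed for the efficacy analysis.
- **Protocol 10.1.4:** define the evaluable count as the efficacy set, that is, subjects with at least 70% adherence and a final OSDI score. State the denominator of the 20% condition. State that the allowance (25 subjects from 101, or 24 from 102) must cover all exclusions, including non-adherence.
- **Protocol 5.3.1:** leave the categories of replaceable subjects unchanged. Adherence exclusions are then counted and reported but not replaced, so no extra enrolment follows.
- **SAP 5.0:** use the same labels, and settle 101 against 51 per arm.
- **Power:** restate it at the expected evaluable number, with the direction of the 1.1-point difference and the one-sided level made explicit. Do not present 102 as giving 80%.

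The cost is wording in a few sections, with no change to procedures or enrolment. The downside is that a stated figure, the power, becomes less favourable.

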#### 10.1.5 Subjects included in the analysis

A preliminary safety analysis will be performed upon completion of follow-up of subject 12 in the Nanodrop® group (Phase I).

If fewer than 20% of unexpected drug-related AEs occur in the Nanodrop® group, enrollment for the efficacy analysis (Phase II) will be completed. Otherwise, the study will be terminated.

For phase II of the study, those subjects who meet a minimum adherence of 70% will be included in the statistical analysis to meet the study objective (PP; per-protocol population).

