$P_g$  = weight of a drop of the intervention, determined by the research and development department

$G$  = number of applications indicated for the investigational products

Packaging that does not maintain its physical integrity will not be considered for the calculation of adhesion.

In cases where the container is not returned, or has not maintained its physical integrity, adherence will be measured using the subject's diary, as follows:

$$Ad = (A_r)100/A_i$$

$Ad$  = Adhesion

$A_r$  = Registered applications

$A_i$  = Applications indicated for investigational products

The "indicated applications for investigational products" will correspond to a minimum dosage of 4 drops per day in each eye, i.e., 8 drops per day for 28 days (224). Because dosage increases are permitted, adherence rates greater than 100% may be observed.

The research center will designate a person responsible for monitoring adherence through a diary during visits. Measuring adherence through weight will be the sponsor's responsibility.

There is no standardized parameter for defining adequate adherence; it must be defined and outlined by the objectives of the particular research. [38]

For this study, a minimum adherence of 70% will be considered necessary to meet the research objectives. Therefore, subjects with less than 70% adherence will not be considered for the efficacy analysis; they will only be included in the safety analysis.

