### 10.1.2 Data interpretation

The Kolmogorov-Smirnov and Shapiro-Wilk tests will be performed, as applicable, to determine whether the distribution is normal in the results obtained in each study group.

The results of continuous quantitative variables will be presented in measures of central tendency: mean, standard deviation and ranges.

The statistical analysis of continuous quantitative variables to find significant differences (  $p<0.05$  ) will be as follows:

- Intra-group analysis: will be determined using the Wilcoxon rank test for quantitative variables.
- Between-group analysis: Differences between groups will be analyzed using the Student t-test or the Mann-Whitney U statistic if applicable ( it will be used to test whether a group of data comes from the same population).

The level of difference considered significant will be an alpha ( $\alpha$ ) of 0.05 or less. A 95% CI will be considered for noninferiority criteria.

The results of the nominal and ordinal qualitative variables will be presented in frequencies, proportions and percentages.

Statistical analysis to identify significant differences in qualitative variables will be performed by creating 2x2 contingency tables and will be carried out as follows:

- Intra-group difference: McNemar's test. This test is applied to 2x2 contingency tables with a dichotomous trait, with matched pairs of subjects, to determine whether the marginal frequencies of the row and column are equal (marginal homogeneity).

- Difference between groups: Pearson's Chi-square test (  $X^2$  ) or Fisher's exact test for expected values less than 5.

The level of difference to consider significance will be an alpha ( $\alpha$ ) of 0.05 or less.

For adverse event reporting, all eyes of participants randomized to an intervention group after the baseline visit will be considered. Results will be expressed as the number of subjects.

The final results report will be displayed in tables or graphs, as appropriate.

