4.0 Sample Size

An estimated 63 subjects (both eyes) per treatment arm are planned (Phase I: 12 subjects / Phase II: 114 subjects).

[figure not shown]

Figure 1. Suggested workflow. ITT: Intention-to-treat population; PP: Per-protocol population.

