The statistical analysis of continuous **quantitative variables** to find significant differences (p) will be as follows:

- Intra-group analysis: will be determined using the Wilcoxon rank test, for quantitative variables (Woolson, 2008).
- Between-group analysis: differences between groups will be analyzed using the Student t-test or the Mann-Whitney U statistic if applicable (it will be used to test whether a group of data comes from the same population).

The level of difference to consider significance will be an alpha (α) of 0.05 or less. It will be considered a 95% CI for non-inferiority criteria (Schumi & Wittes, 2011; Easty et al., 2006).

The result of the nominal and ordinal qualitative variables will be presented in frequencies, proportions and percentages, see table 2.

Statistical analysis to identify significant differences in **qualitative variables** will be performed by creating 2x2 contingency tables and will be carried out as follows:

- Intra-group difference: McNemar's test (Klingenberg & Agresti, 2006). This test is applied to 2x2 contingency tables with a dichotomous trait, with matched subject pairs, to determine whether the marginal frequencies of the row and column are equal (marginal homogeneity).
- Difference between groups: Chi-square test (χ^2) Pearson's or Fisher's exact test in values expected under 5.

The level of difference to consider significance will be an alpha (α) of 0.05 or less.

For the reporting of adverse events, all eyes of participants who were randomized to an intervention group after the baseline visit will be considered.

The final results report will be displayed in tables or graphs, as appropriate.

Subjects who meet a minimum adherence of 70% will be included in the statistical analysis to meet the study objective, based on the weight of the PI. In cases where the container is not returned or has not been physically intact, adherence will be measured using the subject's diary.

The investigational drug will be considered safe and effective when there are no clinical and statistical differences in all primary outcome variables, with respect to its comparator.
(Systaine® Balance).

Table 3. Triangulation of concepts

Variable Type	Variable	A1	B1	B2	C1	C2	D1	E1	E2	E3
Background										
A1	Demographics						DT			
Basal										
B1	Medical record				DT					
B2	Comprehensive ophthalmological evaluation				DT		TB	TB		TB
Security										
C1	Unexpected/related AEs				TB		TB		TB	TB
C2	EAs				TB		TB		TB	TB

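### The OSDI non-inferiority test is assigned only to subjects with at least 70% adherence, a set formed after randomisation, and the visible text gives no all-randomised efficacy analysis to set beside it

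*Protocol*

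**What the plan says.** **Efficacy set.** Protocol 10.1.5 states that for phase II "those subjects who meet a minimum adherence of 70% will be included in the statistical analysis to meet the study objective (PP; per-protocol population". It gives no other criterion. Protocol 10.1.3 has the same rule, with adherence measured by bottle weight and the diary as fallback. SAP 7.0 agrees: "Subjects who meet a minimum adherence of 70% will be included in the statistical analysis to meet the study objective".

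**Subjects below 70%.** Protocol 6.4 is explicit: "subjects with less than 70% adherence will not be considered for the efficacy analysis; they will only be included in the safety analysis". It fixes the denominator at the minimum dose over the full course: "8 drops per day for 28 days (224" in total).

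**ITT.** Protocol 10.1.3 introduces the term under Safety, for subjects exposed at least once, "regardless of the visit at which they were eliminated from the study (ITT; intention-to-treat population"). Protocol 10.1.4 adds, on replacements: "The results obtained from the replaced subjects will continue to be used for safety analysis and will be part of the ITT". No visible sentence attaches ITT to the OSDI. The caption of SAP Figure 1 reads "ITT: Intention-to-treat population; PP: Per-protocol population", but the figure itself is not shown.

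**Decision rule.** Protocol 10.1.2: "A 95% CI will be considered for noninferiority criteria". Whether that interval is one-sided or two-sided is not stated.

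**Follow-up after stopping.** Protocol 5.2.1 lists intolerance of the study product as a reason for elimination. The documents do not say whether a subject who is eliminated or stops product still has the day-29 OSDI taken. Protocol 10.1.3 is headed as missing-data handling but gives no method for a missing score.

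**The concern.** Randomisation makes the two arms comparable as assigned. A filter applied afterwards can undo that if the people it removes differ in outcome and are not removed equally from both arms. Here the filter decides who counts in the primary comparison. A subject who takes the minimum dose, does badly and gives up in the second week is counted for safety but not for efficacy.

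Unequal stopping is plausible but not shown. The products are different formulations, Protocol 7.3 concedes that the subject's blinding cannot be guaranteed, and Protocol 2.2.2 says there is no efficacy information on Nanodrop yet. If subjects who do badly stop more often on Nanodrop, the filter favours non-inferiority. If they stop more often on Systane Balance, it works against it.

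A per-protocol analysis is a normal part of a non-inferiority trial. The difficulty is that here it stands alone: a reader of the report could not tell whether selection had moved the result.

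**Working it through.** **1. What the 70% rule removes.** Protocol 6.4 sets the full count at 8 × 28 = 224 drops, and 0.70 × 224 = 156.8, so 157 drops are needed. At the minimum 8 drops a day, 156.8 / 8 = 19.6 days. A subject on the minimum dose who stops before about day 20 leaves the efficacy set. One who uses extra drops, as Protocol 6.1.3 allows, reaches 157 sooner.

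**2. How selection moves the result.** The plan gives no figure to reproduce on this point, so what follows is an illustration.

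- From the documents: margin 5 points and SD 17.1 (Protocol 10.2.2); 63 randomised per arm (Protocol 10.2.1).
- Assumed: exclusion shares fT (Nanodrop) and fC (comparator). In both arms, excluded subjects score d points worse than included ones. SD stays 17.1 among those included.
- True difference among all randomised subjects: exactly 5 points worse on Nanodrop, so any declaration of non-inferiority is false.

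The included-only deficit is 5 − (fT − fC)·d, so

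- shift = (fT − fC)·d
- SE = 17.1 × √[1/(63(1 − fT)) + 1/(63(1 − fC))]
- P(declare non-inferiority) = Φ(shift/SE − z), with z = 1.960 (two-sided 95% interval) or 1.645 (one-sided).

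| fT | fC | d | shift | SE | two-sided | one-sided |
|---|---|---|---|---|---|---|
| any equal shares | | any | 0 | – | 2.5% | 5.0% |
| 10% | 5% | 5 | 0.25 | 3.169 | 3.0% | 5.9% |
| 10% | 5% | 10 | 0.50 | 3.169 | 3.6% | 6.9% |
| 20% | 10% | 5 | 0.50 | 3.310 | 3.5% | 6.8% |
| 20% | 10% | 10 | 1.00 | 3.310 | 4.9% | 9.0% |
| 10% | 20% | 10 | −1.00 | 3.310 | 1.2% | 2.6% |

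Worked row (20%, 10%, 10 points): shift = 0.10 × 10 = 1.0; SE = 17.1 × √(1/50.4 + 1/56.7) = 3.310; 1.0/3.310 = 0.302; Φ(0.302 − 1.960) = 4.9% and Φ(0.302 − 1.645) = 9.0%.

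**3. Are such shares credible?** The documents give no non-adherence rate. The nearest figure is the allowance for losses in SAP 5.0, 25 of 126 subjects (25/126 = 20%), and that is a loss allowance, not an adherence forecast. Some features may keep the true rate low: 28 days of treatment, exclusion of patients who need Stage 2 management (Protocol 5.1.2), and freedom to add drops (Protocol 6.1.3).

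**The case against.** **ITT may have an efficacy role in SAP Figure 1.** The figure is a suggested workflow whose caption names both sets, and a missing figure is not a gap in the plan. Protocol 10.1.4 can also be read as making ITT more than a safety set, and Protocol 4.2 lists efficacy data from all included subjects as an advantage of the design. This stands as a limit: a reader might infer that the plan has no ITT efficacy analysis anywhere, and the documents cannot establish that. But neither section assigns an analysis set to the OSDI, and a caption does not override the explicit bar in Protocol 6.4.

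**The numbers are assumed.** True. With a 5-point gap the rates stay fairly close to nominal. False non-inferiority is also measured here against all randomised subjects, whereas Protocol 6.4 treats 70% adherence as necessary for the research objectives.

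**Safeguards exist.** Low adherence is not an elimination criterion, OSDI is scheduled at the final visit, and Protocol 5.6 requires sites to contact subjects who miss a visit. Many low adherers should therefore have a day-29 score. That makes the added analysis easier, but as written those scores would not be used for efficacy. Blinding of the analysts limits arm-aware choices; it does not undo outcome-related stopping.

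**The per-protocol set ignores prohibited medication.** A reader might infer that it should also exclude users of medicines prohibited in Protocol 6.3. The documents do not make that a clear defect. Section 6.3 has its own case-by-case route to elimination for non-ophthalmic medicines that could affect the endpoints. That route does not cover prohibited eye drops, but a further exclusion would be one more post-randomisation selection, possibly just as related to outcome. It is a trade-off for the sponsor.

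**Conclusion.** The concern holds on the visible text. Followed as written, the plan rests its primary efficacy conclusion on one set selected after randomisation, with no second analysis to show whether selection mattered. It should be fixed.

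The size is unknown. Under the assumptions tabulated, false non-inferiority ranges from 1.2% to 4.9% against a nominal 2.5% (two-sided interval), or from 2.6% to 9.0% against 5.0% (one-sided). Equal exclusion, with the same outcome gap in both arms, causes no bias.

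A reader might infer that the rule favours Nanodrop. The documents do not support that, because nothing in them says which arm would lose more subjects. Nor do they support a conclusion that non-inferiority must be shown in both sets: that choice carries a real cost in power and belongs to the sponsor.

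**What to change.** 1. **Protocol 10.1.5 and SAP 7.0.** Keep the per-protocol analysis. Add a day-29 OSDI non-inferiority analysis of all randomised subjects as assigned, including replaced subjects. Define this set afresh, because the plan's ITT is described by exposure. State how a missing day-29 score is handled, for example by multiple imputation by arm with a delta-adjusted sensitivity run. Report both analyses, and discuss any disagreement before claiming non-inferiority.
2. **Protocol 6.4 and 10.1.3.** Reword so that subjects below 70% are excluded from the per-protocol analysis only, not from every efficacy analysis.
3. **Protocol 5.2.1.** State that subjects who stop product or are eliminated are still asked to attend for the day-29 OSDI unless they withdraw consent. This must be settled before data accrue, since an uncollected score cannot be recovered.

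**Cost.** One more analysis and a few final visits for subjects who stopped. The OSDI is already scheduled at the final visit, and the sample size need not change.

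**If the sponsor chooses to require both analyses to pass,** the power cost should be known first. At a true difference of 0, SE is 17.1 × √(2/51) = 3.386 for 51 per arm and 17.1 × √(2/63) = 3.047 for 63 per arm. With Φ(5/SE − z), power is 31% for per-protocol alone and 37% for all randomised alone. It is 27% for both, taking correlation √(51/63) = 0.90 and all scores observed. The one-sided figures are 43%, 50% and 39%. Suppose a run adding 5 points to imputed Nanodrop scores must also pass, with 12 of 63 imputed. The shift is 5 × 12/63 = 0.95, and joint power falls to about 22% (33% one-sided), before any imputation variance.
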